8.4.4 Vital Signs

For treatment emergent vital signs measurements, the raw values and changes from baseline will be summarized by treatment group at each scheduled time point for systolic and diastolic blood pressure (mmHg), body temperature ($^{\circ}\text{C}$), HR (beats per minute), and respiratory rate (breaths per minute). In addition, the mean value at each time point will be plotted by treatment group for systolic and diastolic blood pressure.

The number and percentage of subjects with vital signs meeting threshold criteria during the treatment-emergent period will be summarized by treatment, vital signs parameters, and visit. The threshold criteria are provided in Section 11.5, Table 11-9.

8.4.5 Pulse Oximetry

A summary of raw values and change from baseline values will be provided by treatment group at each scheduled time point for the percent of oxygen saturation by pulse oximetry. In addition, the mean value at each visit will be plotted by treatment group for the percent of oxygen saturation.

The number and percentage of subjects with shift changes from baseline (normal/missing and low according to the reference range) to the lowest percent of oxygen saturation during the treatment-emergent period will be tabulated by treatment groups.

8.4.6 Postdose Spirometry

For subjects < 18 years old at screening, a summary of the raw values and change from pre-dose value for percent predicted FEV₁ will be provided by treatment group at each time point (2-hour and 4-hour postdose) on Day 1 and Day 15. In addition, a box plot by study day and treatment group will be provided for each time point.

The above analyses will be repeated for FEV₁ [in L]

In addition, the number and percentage of subjects with percent predicted FEV₁ decline ≥ 10 , ≥ 15 , and ≥ 20 percentage points in the absolute change from the predose value will be summarized by treatment arm and by assessment day and time. The number and percentage of subjects with ≥ 0.20 L decrease from baseline in FEV₁ will be summarized by treatment arm and by assessment day and time.

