12.3.4.6.2 Postdose Spirometry

For the 2-hour and 4-hour postdose measurements on Day 1 and Day 15, a summary of raw values for percent predicted FEV₁ will be provided by treatment group at each time point.

The absolute change from the predose value of percent predicted FEV₁ on the same day will be provided by treatment group at each time point. In addition, a box plot by time point will be provided. Within each treatment group, Day 1 and Day 15 values will be presented on the same plot.

The above analyses will be repeated for FEV₁.

In addition, the number and percentage of subjects with percent predicted FEV₁ decline ≥ 10 , ≥ 15 , and ≥ 20 percentage points in the absolute change from the predose value will be summarized by treatment arm and by assessment day and time.

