8 STATISTICAL ANALYSIS

8.1 General Considerations

All individual subject data in the All Subject Set will be presented in data listings. The Schedule of Assessments is provided in Section 11.1. The precision standards are provided in Section 11.6.

Continuous variables will be summarized using the following descriptive summary statistics: the number of subjects (n), mean, standard deviation (SD), median, minimum value (min), and maximum value (max).

Categorical variables will be summarized using counts and percentages.

Baseline Value, unless otherwise specified, is defined as the most recent non-missing measurement (scheduled or unscheduled) collected prior to or on the first dose of study drug. For ECGs, the baseline will be defined as the average of the 3 pre-treatment measurements (triplicate) on Day 1. For sweat chloride, the baseline value will be the mean of last assessment values on the left and the right arm prior to the first dose of the study drug.

Change (Absolute Change) from baseline will be calculated as Post-baseline value – Baseline value.

Relative change from baseline will be calculated and expressed in percentage as $100 \times (\text{Post-baseline value} - \text{Baseline value}) / \text{Baseline value}$.

Treatment Emergent (TE) Period will include the time from the first dose of study drug to the Safety Follow-up Visit, or to 28 days after the last dose of the study drug for subjects who do not have a Safety Follow-up Visit, or to the last participation date in the study (i.e., the day right before the first study dose in the extension study for subjects who enrolled into the extension study), whichever occurs first. The TE period will be used for safety analyses unless otherwise specified.

Unscheduled Visits: Unscheduled visit measurements will be included in the following:

1. derivations of measurements at scheduled visits per specified visit windowing rules below;
2. derivations of baseline/last on-treatment measurements;
3. derivations of the maximum/minimum on-treatment values and maximum/minimum changes from baseline values for safety analyses;
4. data listings where appropriate.

Visit Windowing Rules: Section 11.2 defines the windows for protocol-defined visits. The windows will be applied using the following rules for both scheduled and unscheduled visits:

1. If no measurement is available within a visit window, the assessment will be considered missing for the visit;

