8.4 Safety Analysis

All safety analyses will be based on the Safety Set. Subjects will be analyzed according to the treatment they actually received if they took the same study drug during the entire study period. For subjects receiving study drug from more than one treatment group by error, the treatment group allocation will be TEZ/IVA.

The overall safety profile of study drug will be assessed in terms of the following safety and tolerability endpoints:

- Adverse events
- Clinical laboratory values (hematology, serum chemistry, coagulation studies, vitamin levels, lipid panel, and urinalysis)
- Standard 12-lead electrocardiograms
- Vital signs
- Pulse oximetry
- Postdose ppFEV₁ and FEV₁ (L) and change from predose.

Safety endpoints will be analyzed using data during the treatment emergent period. Only descriptive summaries will be presented and no statistical testing is planned.

Treatment Emergent (TE) Period will include the time from the first dose of study drug to the Safety Follow-up Visit, or to 28 days after the last dose of the study drug for subjects who do not have a Safety Follow-up Visit, or to the last study participation day (i.e., the day right before the first study dose in the extension study for subjects who enrolled into the extension study), whichever occurs first.

For the purpose of safety analyses, the entire study period will then be further divided into 3 segments:

- The **pre-treatment period** is the period after the informed consent/assent date and before the start date of the TE period.
- The **treatment-emergent period** (TE period) is defined as above.
- The **post-treatment period** is the period after the end of the TE period to the date of the last study record in the clinical database.

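### SAP 8.4.6 counts post-dose FEV1 falls of at least 0.20 L from study baseline, not from the same-day pre-dose value, so the Day 15 count mixes change since baseline with the acute response

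*SAP*

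**What the plan says.** SAP 8.4.6 covers spirometry at 2 and 4 hours post-dose on Day 1 and Day 15 in subjects under 18 at screening. It summarizes raw values and change from pre-dose, with box plots, for percent predicted FEV1 (ppFEV1), and repeats this in litres. Two threshold counts follow:

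- ppFEV1 declines of at least 10, 15 and 20 "percentage points in the absolute change from the predose value".
- In the next sentence, the count of subjects with at least a 0.20 "L decrease from baseline in FEV₁ will be summarized by treatment arm and by assessment day and time".

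SAP 8.1 says that baseline, unless otherwise specified, "is defined as the most recent non-missing measurement (scheduled or unscheduled) collected prior to or on the first dose of study drug". SAP 8.4.6 specifies nothing else, so baseline there means study baseline.

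The other relevant text points to pre-dose. SAP 8.4 lists the safety endpoint as post-dose ppFEV1 and FEV1 in litres "and change from predose". Protocol 12.3.4.6.2 states: "The absolute change from the predose value of percent predicted FEV₁ on the same day will be provided by treatment group". The protocol has no 0.20 L count. SAP 8.5.1 separately counts 0.20 L falls from baseline for pre-dose spirometry at each visit.

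**The concern.** Post-dose spirometry at 2 and 4 hours measures what happens after a dose. Protocol 8.2.4 says that it was added for subjects under 18 at a regulator's request. A threshold count serves that purpose only if its reference is the value just before the dose.

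On Day 15 study baseline is about two weeks old. Protocol 8.2.1 anticipates an FEV1 response after 14 to 28 days, so some active-arm subjects may already have gained. Such a subject must fall by 0.20 L plus the gain to be counted, while a placebo subject with no gain need fall only 0.20 L. The between-arm comparison in the Day 15 cells would then lean towards active drug. Ordinary day-to-day variation would also move subjects in and out of the count in both arms, whatever the dose did.

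**Working it through.** The documents attach no figure to the 0.20 L count, so there is none to reproduce. The check is an identity, a conversion and an illustration.

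**1. Identity for Day 15.**

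Post-dose − baseline = (pre-dose − baseline) + (post-dose − pre-dose) = C + A

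C is the change since baseline and A is the acute change. The ppFEV1 counts use A. The litre count as written uses C + A. On Day 1 baseline is normally the same-day pre-dose value, so C = 0 and the two agree.

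**2. Size in litres.** The Wang coefficients in SAP 11.3 (white subjects) give predicted FEV1 = exp(α + β ln height). Heights are assumed.

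| Subject | Assumed height (m) | Predicted FEV1 (L) | 2.5 points in L | 0.20 L in points |
|---|---|---|---|---|
| Girl, 12 | 1.46 | 2.14 | 0.054 | 9.3 |
| Boy, 12 | 1.45 | 2.16 | 0.054 | 9.2 |
| Girl, 15 | 1.58 | 2.91 | 0.073 | 6.9 |
| Boy, 15 | 1.65 | 3.37 | 0.084 | 5.9 |
| Boy, 17 | 1.72 | 4.06 | 0.101 | 4.9 |

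The 2.5 points are the design difference in SAP 6.2, used only to set a scale. A subject with that gain by Day 15 needs an acute fall of about 0.25 to 0.30 L to be counted. The 10-point ppFEV1 cut is about 0.21 to 0.41 L over the same range.

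**3. Illustration.** The documents give no litre SDs and no Day 15 gain, so all of these are assumed: gain g = 0.0875 L on active (2.5% of an assumed 3.5 L predicted value) and 0 on placebo, SD(A) = 0.12 L, SD(C) = 0.20 L. With A and C independent normal, SD(C + A) = √(0.12² + 0.20²) = 0.233 L.

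*No acute effect in either arm:*
- From pre-dose, both arms: Φ(−0.20/0.12) = 4.8%.
- From baseline, active: Φ(−0.2875/0.233) = 10.9%.
- From baseline, placebo: Φ(−0.20/0.233) = 19.6%.

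*Mean acute fall of 0.0875 L on active, none on placebo:*
- From pre-dose: active Φ(−0.1125/0.12) = 17.4%, placebo 4.8%.
- From baseline: 19.6% in both arms, because the assumed fall cancels the assumed gain exactly.

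With g from 0.05 to 0.10 L, SD(A) from 0.10 to 0.15 L and SD(C) from 0.15 to 0.25 L, the spurious gap with no acute effect is about 5 to 10 points in favour of active drug. When the acute fall equals the gain, a true gap of about 4 to 16 points becomes zero.

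**4. A case without exact cancellation.** Active: mean acute fall 0.10 L, mean gain 0.08 L. Placebo: both zero.

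| SD(A), SD(C) in L | From pre-dose, active vs placebo | From baseline, active vs placebo |
|---|---|---|
| 0.10, 0.15 | 15.9% vs 2.3% | 15.9% vs 13.4% |
| 0.15, 0.25 | 25.2% vs 9.1% | 26.8% vs 24.6% |

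The gap shrinks from about 14 to 16 points to 2 to 3 points.

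**5. Misclassification of individuals.** Simulation with 1,000,000 draws per scenario, mean acute change 0 to −0.20 L and the SD values of step 4 in all combinations. With a mean gain of 0.08 L, about 42 to 61% of subjects with a true same-day fall of at least 0.20 L are not counted. With no mean gain, visit-to-visit variation alone loses about 25 to 44%. At a gain of 0.08 L, about 18 to 93% of those counted had no acute fall of 0.20 L.

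**The case against.** A reader might infer that an acute drop on active drug would be invisible, or that the plan does not measure acute respiratory safety. The documents do not support that. SAP 8.4.6 reports the litre change from pre-dose at 2 and 4 hours on both days, with box plots, so a mean fall of the size in step 3 would appear there directly. The ppFEV1 counts use pre-dose, and respiratory adverse events are tabulated by treatment interval (SAP 8.4.1.8). Day 1, the first-dose response, is normally unaffected. The table is descriptive, confined to subjects under 18, and SAP 8.4 plans no testing. All of this stands.

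It also stands that the percentages are illustrative. The design difference is defined through Week 24, and a smaller Day 15 gain shrinks the bias. The exact cancellation in step 3 is built in.

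Two further arguments carry less weight. First, a count from baseline answers a legitimate question: whether a subject after dosing is well below the starting level. That justifies a labelled extra count, but it is not the endpoint in SAP 8.4. Second, baseline may be a drafting slip for pre-dose. That is plausible given the preceding sentence, but a programmer applying SAP 8.1 would use study baseline. The protocol has no litre count to settle the matter, and SAP Section 3 says that the SAP prevails where its methods differ from the protocol's.

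**Conclusion.** The point holds for one set of cells: the Day 15 count of FEV1 falls of at least 0.20 L. As written, its reference differs from that of the adjacent ppFEV1 counts, the SAP 8.4 endpoint and protocol 12.3.4.6.2. If active-arm subjects have gained FEV1 by Day 15, the count understates their acute falls relative to placebo. Misclassification through visit-to-visit variation affects both arms even without a gain.

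What is lost is a valid post-dose threshold count in litres at Day 15. The continuous summaries do not fully replace it, because they show the average and spread and do not tabulate how many subjects cross 0.20 L. The ppFEV1 counts start at 10 points, above the roughly 5 to 9 points that 0.20 L represents at predicted values of 2.1 to 4.1 L. For the smallest subjects the two cuts nearly meet (0.20 against about 0.21 L); for larger adolescents they are well apart.

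The identity needs no assumptions. The direction of the between-arm bias requires a Day 15 gain on active drug. The percentages rest on the assumed gain, SDs, heights and normal model. This is worth correcting before unblinding, but it does not touch an efficacy claim or a decision rule.

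**What to change.** In SAP 8.4.6, refer the 0.20 L count to the same-day pre-dose FEV1 instead of baseline, by assessment day and time as now. If the sponsor also wants to know who is at least 0.20 L below the starting level after dosing, keep that as a second count, labelled as change from study baseline. SAP 8.5.1 stays as it is.

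The cost is one phrase in the SAP and one reference value in the table program. The Day 1 and Day 15 pre-dose and post-dose measurements are already scheduled, so no new data are needed.

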8.4.7 Physical Examination

PE findings will be presented in a data listing only.

8.4.8 Ophthalmology Examination

Ophthalmologic findings (cataracts) during the treatment-emergent period will be summarized by treatment group. The numbers and percentages of subjects with cataract at screening will be presented. The numbers and percentages of subjects with cataract after the first dose of study drug will be presented. In addition, ophthalmology examination results will be provided in a data listing for subjects who have developed any cataracts during the treatment-emergent period. Subjects with cataract at screening will also be listed.

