- A subject develops a cataract or lens opacity.

Subjects who discontinue study treatment early should continue to return for assessments as noted in Section 8.1.4.

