11.7.8 Ophthalmologic Examination

Subjects will undergo an ophthalmologic examination performed by a licensed ophthalmologist at Screening, which includes

- measurement of best corrected distance visual acuity of each eye
- measurement of lens refracting power following cycloplegia (e.g., autorefractor or ophthalmoscopy streak)
- pharmacologically dilated examination of the lens with a slit lamp

The screening ophthalmologic examination must be completed and the results reviewed before randomization. This examination does not have to be repeated if there is documentation of an examination that met protocol criteria and that was within 3 months before the start of the Screening Period.

If a cataract, lens opacity, Y-suture, or lamellar rings are identified and determined to be clinically significant by the ophthalmologist at the Screening examination, the subject is ineligible for study entry (See Section 9.2). If a cataract or lens opacity is identified and determined to be clinically significant by the ophthalmologist after dosing, the subject and Vertex medical monitor will be notified. After discussion with the principal investigator, who collaborates with the Vertex medical monitor, the subject may elect to continue or discontinue study drug treatment. If the subject discontinues study drug treatment, the subject should complete the ETT and Safety Follow-up Visits (see Section 8.1.4). If the subject continues study drug treatment, more frequent ophthalmologic monitoring should be considered.

In addition to the screening examination, all subjects will have an ophthalmologic examination conducted by a licensed ophthalmologist at Week 24. This exam may be completed within 4 weeks before the Week 24 Visit, but must be completed by the end of the Week 24 Visit.

In addition, an ophthalmologic examination will be performed by a licensed ophthalmologist at the Safety Follow-up Visit or ETT Visit for the following subjects:

- subjects <18 years of age at the Screening Visit who discontinue treatment after receiving at least 1 dose of study drug
- subjects <18 years of age at the Screening Visit who complete treatment but do not enroll in a separate extension study of VX-661/ivacaftor within 28 days of the last dose of study drug

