This examination may be completed at either the ETT or Safety Follow-up Visit, but must be completed by the end of the Safety Follow-up Visit. Subjects <18 years of age at the Screening Visit are only required to complete 1 ophthalmologic exam at the end of treatment (Week 24 Visit, ETT Visit, or Safety Follow-Up Visit), as described in Table 3-2.

Subjects \geq 18 years of age at the Screening Visit are not required to complete the ETT or Safety Follow-Up Visit ophthalmologic exams.

Additional ophthalmologic examinations may be conducted at the discretion of the investigator. The medical monitor should be notified of any additional ophthalmologic examinations.

In addition, at Screening, the following history will be obtained for all subjects:

- history of steroid use
- history or presence of diabetes
- any prior ophthalmologic or optometric examinations
- history of trauma to the eye
- any family history of glaucoma, congenital cataracts, or cataracts arising later in life
- use of corrective lenses (contact lenses or eyeglasses)
- history of prolonged exposure to sunlight or ultraviolet light and use of sunglasses
- history of exposure to secondhand smoke

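### The SAP's cataract summary and listing can miss the only required post-dose lens examination of adults who stop drug well before Week 24, do not isolate new cases, and leave out lens opacity

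*SAP*

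**What the plan says.** SAP 8.4.8 is the only visible specification of an eye-examination analysis; the visible text of protocol 12.3.4 has none. It sets out these outputs:

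- A summary by arm: "Ophthalmologic findings (cataracts) during the treatment-emergent period will be summarized by treatment group".
- A screening count, "The numbers and percentages of subjects with cataract at screening will be presented", with a listing: "Subjects with cataract at screening will also be listed".
- A post-dose count: "The numbers and percentages of subjects with cataract after the first dose of study drug will be presented".
- A listing of examination results "for subjects who have developed any cataracts during the treatment-emergent period".

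The section does not define cataract, state a denominator, or specify a new-onset or shift table. SAP 8.4 bases safety analyses on the Safety Set and on TE data. SAP 8.1 applies the TE period to safety analyses unless something else is specified. The period ends at the Safety Follow-up Visit or, without one, 28 days after the last dose. For subjects entering the extension it ends no later than the day before the first extension dose.

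Protocol 11.7.8 requires that, beyond screening, "all subjects will have an ophthalmologic examination conducted by a licensed ophthalmologist at Week 24", and allows this up to 4 weeks before the visit. Subjects under 18 who stop early are examined at ETT or Safety Follow-up. Subjects aged 18 or over "are not required to complete the ETT or Safety Follow-Up Visit ophthalmologic exams". Among the possible reasons for withdrawing study drug, protocol 9.5 lists: "A subject develops a cataract or lens opacity". Exclusion criterion 6 in protocol 9.2 applies only to lens findings judged clinically significant.

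**The concern.** The protocol gives lens findings their own exclusion criterion, a place in the treatment-withdrawal list and a dedicated examination section. A reader of the study report will want to know how many subjects in each arm developed a lens finding after starting drug, out of those examined. The outputs in SAP 8.4.8 do not give that number, for three reasons:

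- For some adults the one scheduled post-dose examination lies after the TE period closes.
- The post-dose count may mix cataracts already present at screening with new ones.
- Lens opacity has no place in the table.

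These are likely to be uncommon findings, so a single case left out or wrongly included could change how the table reads. If early stopping differed between arms, the arms would also differ in how completely they were observed. That last point is a possibility; nothing in the documents shows that it will happen.

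**Working it through.** The plan gives no figure to reproduce here. The check is date arithmetic, followed by a comparison of the texts.

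**1. When the Week 24 examination falls outside the TE period**

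Inputs:
- Week 24 target day: 7 × 24 + 1 = Day 169 (day convention in protocol Section 3; target day in SAP 11.2).
- Earliest examination for a visit on that day: 169 − 28 = Day 141 (protocol 11.7.8).
- TE tail after last dose: 28 days without a Safety Follow-up Visit (SAP 8.1, 8.4). With one, 28 ± 7, so 21 to 35 days (protocol 8.1.4).

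The examination is outside TE when examination day > last-dose day + tail, that is, when last-dose day < examination day − tail.

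| Examination day | Tail 21 days | Tail 28 days | Tail 35 days |
|---|---|---|---|
| 169 | before Day 148 | before Day 141 | before Day 134 |
| 141 | before Day 120 | before Day 113 | before Day 106 |

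For a Week 24 visit on its target day, the cut-off therefore lies between Day 106 (15 weeks of dosing) and Day 148 (21 weeks). The ±5-day visit window widens this:
- Visit on Day 164, examination 28 days earlier, 35-day tail: 164 − 28 − 35 = Day 101.
- Visit and examination on Day 174, 21-day tail: 174 − 21 = Day 153.

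For comparison, a completer with last dose on Day 168 who does not enter the extension has a TE period ending between 168 + 21 = Day 189 and 168 + 35 = Day 203, so the examination is inside. Subjects under 18 who stop early are due an examination by Safety Follow-up, which normally keeps it inside TE as well. The gap therefore concerns adults who stop well before Week 24.

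**2. Which period governs the post-dose count**

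The summary sentence and the listing of developed cataracts both name the TE period. The post-dose count names only a start, the first dose. Under SAP 8.1 the silence could be read as the default (TE applies) or as an exception (all post-dose data). Two programmers could produce different counts for the same adult.

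**3. Whether new cases can be recovered from the two counts**

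Let S be the number of subjects with cataract at screening and A the number with cataract after first dose. A subject with a non-significant cataract can enrol and be counted in both. Without a cross-tabulation, the number of new cases lies anywhere from max(0, A − S) to A, because the counts do not show how many of the S subjects were examined again. Worsening of an existing cataract appears in neither count.

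**4. Scope of the finding**

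Protocol 9.2, 9.5 and 11.7.8 each name lens opacity as well as cataract. SAP 8.4.8 names cataract alone, with no definition that takes in opacities.

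**5. Whether adults who stop early are due the Week 24 examination**

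Protocol 11.7.8 and Table 3-2 assign it to all subjects. The Table 3-2 footnote waives it only for under-18s already examined at ETT. Protocol 8.1 requires assessments at all scheduled visits whether or not drug was stopped. The visible part of the list in protocol 8.1.4 names efficacy and outcome assessments and not the eye examination, but part of that list is redacted.

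**The case against.** The strongest reply is that this is a descriptive table, with no testing, for something that is not on the list of safety endpoints, and that protocol 12.3.4 pre-specifies the TE period for safety. The individual data are not hidden: SAP 8.1 lists all subject data, clinically significant worsening can be recorded as an adverse event, and protocol 11.7.8 allows extra examinations at the investigator's discretion. All of this stands, and it keeps the point modest. None of it supplies a count by arm of new findings from the scheduled examinations.

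Several stronger readings are tempting, and the documents do not support them:

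- *Every adult who stops early loses the examination.* Those who stop after the cut-off in the working keep it inside TE.
- *Late examinations are certainly excluded.* They fall outside the TE summary and listing, but the count after first dose could include them if read literally. For that count the fault is ambiguity.
- *Screening cataracts are not reported separately.* They have their own count, percentage and listing. The gap is that the post-dose count is not restricted to new cases.
- *Unexamined subjects are counted as free of cataract.* SAP 8.4.8 states no denominator. A Safety Set denominator, which SAP 8.4 suggests, would dilute the percentage, but that is an inference.
- *The protocol contradicts itself on the Week 24 examination.* With part of 8.1.4 redacted, and with 8.1, 11.7.8 and Table 3-2 pointing to all subjects, this is a point to confirm.

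**Conclusion.** The point holds as an inexpensive improvement to a descriptive safety table. For an adult whose last dose is well before Week 24, the only required post-dose lens examination lies outside the TE summary and listing. The cut-off is Day 141 for a Day 169 examination with a 28-day tail, and Day 106 to Day 148 across the examination and follow-up timings allowed around a Day 169 visit. The post-dose count has an unclear end date and is not limited to new or worsened cases, and lens opacity is left out.

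The number of adults affected cannot be derived. A reader might take 10% of 490 = 49 subjects, but that 10% is the dropout allowance in the sample-size section. It is not a rate of stopping treatment, and the protocol keeps subjects who stop drug in the study. A subject who leaves the study has no Week 24 examination for the TE rule to discard. The documents give neither the share of adults nor the timing of discontinuation. The arithmetic assumes that the Week 24 examination is done in adults who stop early, as protocol 11.7.8 states.

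**What to change.** In SAP 8.4.8:

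- Keep the screening count and listing.
- Add, by arm, the number and percentage of subjects with a new or worsened cataract or lens opacity relative to the screening examination, at any examination after first dose through Week 24 or Safety Follow-up. A TE-only version can stand beside it.
- Use as denominator the subjects with at least one post-dose lens examination, and show that number.
- List the same subjects.

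Reconcile the visible text of protocol 8.1.4 with 11.7.8 and Table 3-2 on the Week 24 lens examination for adults who stop early, or confirm that the redacted text already does so.

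The cost is SAP wording, one more derivation and, if needed, a clarifying sentence in the protocol. The analysis uses examinations that 11.7.8 already schedules. The drawback is that some findings made well after the last dose enter the count, which is the reason for offering the TE-only version alongside.
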